8.4. Emergency Unblinding of Treatment Assignment

Not applicable.

8.5. Adverse Events of Special Interest

Specific AEs, or groups of AEs, will be followed as part of standard safety monitoring activities.

- $ALT \geq 5 \times ULN$
- $AST \geq 5 \times ULN$
- Colitis
- Diarrhea \geq Grade 2
- Intestinal perforation
- Rash \geq Grade 2
- Exfoliative dermatitis
- Pneumonitis
- PJP infection
- CMV infection
- Herpes simplex virus infection
- Varicella zoster virus infection

8.6. Pregnancy

Pregnancy, in and of itself, is not regarded as an AE unless there is suspicion that study drug may have interfered with the effectiveness of a contraceptive medication or method. When a

pregnancy has been confirmed in a subject during maternal or paternal exposure to study drug, the following procedures should be followed in order to ensure subject safety:

- The study drug must be discontinued immediately (female subjects only; see Section 5.4.1 for the maximum permitted duration of study drug interruption).
- The investigator must complete and submit the Incyte Clinical Trial Pregnancy form to the sponsor or its designee within **24 hours** of learning of the pregnancy.

Data on fetal outcome and breastfeeding are collected for regulatory reporting and drug safety evaluation. Follow-up should be conducted for each pregnancy to determine outcome, including spontaneous or voluntary termination, details of the birth, and the presence or absence of any birth defects, congenital abnormalities, or maternal and/or newborn complications, by following until the first well-baby visit. Pregnancy should be recorded on a Clinical Trial Pregnancy form and reported by the investigator to the sponsor or its designee. Pregnancy follow-up information should be recorded on the same form and should include an assessment of the possible causal relationship to the sponsor's study drug to any pregnancy outcome, as well as follow-up to the first well-baby visit or the duration specified in local regulations, whichever is later. Refer to the Incyte Reference Guide for Completing the Clinical Trial Pregnancy Form.

Any SAE occurring during pregnancy must be recorded on the SAE report form and submitted to the sponsor or designee.

8.7. Warnings and Precautions

Special warnings or precautions for the study drug, derived from safety information collected by the sponsor or its designee, are presented in the IB. Additional safety information collected between IB updates will be communicated in the form of INs. Any important new safety information should be discussed with the subject during the study, as necessary. If new significant risks are identified, they will be added to the ICF.

8.8. Independent Data Monitoring Committee

An IDMC will be formed and will consist of qualified individuals who are not involved with the conduct of the study. The establishment, composition, roles, duties, and responsibilities of the IDMC are addressed in the approved IDMC charter.

8.9. Product Complaints

The sponsor collects product complaints on study drugs and drug delivery systems used in clinical studies in order to ensure the safety of study participants, monitor quality, and facilitate process and product improvements.

All product complaints associated with material packaged, labeled, and released by the sponsor or its designee will be reported to the sponsor. All product complaints associated with other study material will be reported directly to the respective manufacturer.

The investigator or his/her designee is responsible for reporting a complete description of the product complaint via email or other written communication to the sponsor contact or respective manufacturer as noted in the packaging information. Any AE associated with a product complaint should be reported as described in Section 8.1.2 of this Protocol.

If the investigator is asked to return the product for investigation, he/she will return a copy of the product complaint communication with the product.

9. STATISTICS

9.1. Study Populations

The full analysis set includes all subjects enrolled in the study who received at least 1 dose of INCB050465. The full analysis set will be used for the summary of demographics, baseline characteristics, subject disposition, and analyses of all efficacy data.

The safety population includes the same set of subjects as the full analysis set. This population will be used for all safety analyses.

9.2. Selection of Sample Size

Cohort 1: Will be closed to further enrollment with Protocol Amendment (Version) 3.

Cohort 2: Up to 90 subjects will be enrolled. If the true ORR is 60%, then there is approximately 90% or 96% probability of observing the lower bound of the 95% CI of ORR $\geq 40\%$ with 60 or 90 subjects, respectively.

9.3. Level of Significance

There will not be any statistical comparison between Cohort 1 and Cohort 2. Within each of the 2 cohorts, 2-sided 95% CIs will be reported for all analyses when appropriate.

9.4. Statistical Analyses

All analyses will be conducted independently for Cohort 1 and Cohort 2, and there will not be multiplicity adjustment between the cohorts.

Within each of the 2 cohorts, efficacy data from the 2 treatment regimens (A and B) will be combined for the purpose of the primary and secondary efficacy analyses. Safety data will be summarized by treatment regimen and combined.

9.4.1. Efficacy Analyses

9.4.1.1. Primary Efficacy Analyses

Objective response rate is defined as the percentage of subjects with a CR or PR as determined by revised response criteria for lymphomas (Cheson et al 2014).

The ORR as determined by the IRC and its 95% exact binomial CIs will be calculated. This is considered the primary efficacy analysis for each of the 2 cohorts.

The ORR as reported by the investigator and its 95% exact binomial CIs will also be calculated.

Response data will be analyzed when all subjects in the full analysis set of the respective cohort have reached at least 1 postbaseline disease assessment or have progressed, withdrawn from the study, or died.

9.4.1.2. Secondary Efficacy Analyses

Duration of response is defined as the time from first documented evidence of CR or PR until disease progression or death due to any cause among subjects who achieve an overall response (ie, CR or PR) as determined by revised response criteria for lymphomas (Cheson et al 2014). For subjects who have not progressed and are still alive at the time of the analysis, DOR will be censored on the day of last evaluable disease assessment. For subjects who have discontinued study or have started other anticancer treatment, DOR will be censored on the day of last evaluable disease assessment documenting absence of PD before the discontinuation or the start of the new anticancer treatment.

Progression-free survival is defined as the time from the date of first dose of the study drug to the first documented disease progression as determined by revised response criteria for lymphomas (Cheson et al 2014), or death due to any cause, whichever occurs first. For subjects who have not progressed and are still alive at the time of the analysis, PFS will be censored on the day of last evaluable disease assessment. For subjects who have discontinued study or have started other anticancer treatment, PFS will be censored on the day of last evaluable disease assessment documenting absence of PD before the discontinuation or the start of the new anticancer treatment. For subjects who have no baseline or no postbaseline disease assessment, PFS will be censored with censored duration of 1 day.

The Kaplan-Meier estimation of median DOR and PFS as determined by the IRC and its 95% CIs will be provided.

Complete response rate is defined as the percentage of subjects with a CR as determined by revised response criteria for lymphomas (Cheson et al 2014).

The CRR as determined by the IRC and its 95% exact binomial CIs will be calculated.

Overall survival is defined as the time from the date of first dose of study drug to death due to any cause. For subjects who are still alive at the time of the analysis, OS will be censored on the date the subjects is last known to be alive. The Kaplan-Meier estimation of median OS and its 95% CIs will be provided.

Target lesion size is measured by the sum of the product of diameters of all target lesion sizes. Best percentage change in target lesion size from baseline will be summarized descriptively.

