## **7.4. Analysis of the Secondary Efficacy Parameters**

### **7.4.1. Duration of Response**

Duration of response is defined as the time from first documented evidence of CR or PR until disease progression or death due to any cause among participants who achieve an objective response (ie, CR or PR), as determined by revised response criteria for lymphomas ([Cheson et al 2014](#)). For responses assessed by IRC, the date of initial response and date of disease progression will be provided by the clinical reviewer for participants who have achieved best response of CR or PR. Censoring of DOR will follow the same algorithm as the censoring of PFS (Section 7.4.3).

The total number of responders as determined by IRC, the number of participants whose disease progressed as determined by IRC or who died, and the number of participants censored will be summarized. The Kaplan-Meier estimate of median DOR as determined by IRC and its 95% CIs will be provided, with the CIs calculated using the generalization of Brookmeyer and Crowley's method ([1982](#)) with log-log transformation ([Klein and Moeschberger 1997](#)).

A sensitivity analysis of DOR will be performed where response assessments after the time of crossover will be excluded from the determination of DOR for participants who switched to the selected treatment regimen after starting the maintenance dose. Crossover participants who have not progressed at the time of crossover will be censored at the last valid radiologic assessment on/before the time of crossover. Participants who failed to achieve a response of CR or PR on/before the time of crossover will not be considered as responders for this analysis.

The analyses described above will be summarized for all participants and participants who have at least 2 prior therapies in the FAS.

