### 7.4.3. Progression-Free Survival

Progression-free survival is defined as the time from the date of the first dose of the study drug to the first documented disease progression as determined by revised response criteria for lymphomas (Cheson et al 2014), or death due to any cause, whichever occurs first. For response assessed by IRC, date of disease progression will be provided by the clinical reviewer. Censoring for PFS will follow the algorithm outlined in Table 2, which is based on FDA Guidance for Industry: Clinical Trial Endpoints for the Approval of Non-Small Cell Lung Cancer Drugs and Biologics (2015) and Guidance for Industry: Clinical Trial Endpoints for the Approval of Cancer Drugs and Biologics (2018).

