**Table 2: Evaluation and Censoring of Progression-Free Survival**

Situation	Outcome	Date of Progression or Censoring
No baseline tumor assessments	Censored	Day 1
No valid postbaseline response assessments	Censored	Day 1
Progression documented between scheduled response assessments	Progressed	Date of first overall response of PD
No progression	Censored	Date of last valid radiologic assessment (not NE and not missing)
Study discontinuation for undocumented progression	Censored	Date of last valid radiologic assessment (not NE and not missing)
Study discontinuation for toxicity or other reason	Censored	Date of last valid radiologic assessment (not NE and not missing)
New anticancer treatment started	Censored	Date of last valid radiologic assessment (not NE and not missing) on/before starting a new anticancer treatment
Death before first progressive response assessment	Progressed	Date of death
Death between adequate response assessments	Progressed	Date of death
Death or progression after 2 or more missed assessments	Censored	Date of last valid radiologic assessment (not NE and not missing) before the missed assessments

NE = not evaluable.

The total number of participants whose disease progressed as determined by IRC or who died and the number of participants censored will be summarized. The Kaplan-Meier estimate of median PFS as determined by IRC and its 95% CIs will be provided, with the CIs calculated using the generalization of Brookmeyer and Crowley's method (1982) with log-log transformation (Klein and Moeschberger 1997). Progression-free survival rates at Month 6, 12, 18, 24, and 36 will also be provided with 95% CIs calculated using Greenwood's formula to estimate the standard error.

A sensitivity analysis of PFS will be performed where response assessments after the time of crossover will be excluded from the determination of PFS for participants who switched to the selected treatment regimen after starting the maintenance dose. Crossover participants who have not progressed at the time of crossover will be censored at the last valid radiologic assessment on/before the time of crossover.

The analyses described above will be summarized for all participants and participants who have at least 2 prior therapies in the FAS.

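### SAP Table 2 gives two codings for a death before any valid scan, and its missed-assessment censoring of PFS and DOR is an undeclared departure from the Protocol

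*Protocol*

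**What the plan says.** **Definition.** SAP Section 7.4.3 runs PFS from first dose to first documented progression "or death due to any cause, whichever occurs first". Protocol Section 9.4.1.2 defines it the same way.

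**No-scan rule.** Protocol Section 9.4.1.2: "For subjects who have no baseline or no postbaseline disease assessment, PFS will be censored with censored duration of 1 day". The general censoring sentence in the same paragraph is limited to subjects who are alive without progression; this one is not. SAP Table 2 has two matching rows, one for no baseline assessment and one for "No valid postbaseline response assessments". Both are censored at Day 1.

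**Death rows.** Table 2 also lists "Death before first progressive response assessment", coded as progressed at the date of death. It does not ask for an earlier valid scan. The table gives no row order.

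**Missed assessments.** Table 2 lists "Death or progression after 2 or more missed assessments", censored at the last valid scan before the gap. SAP Section 7.4.1 extends this to DOR: "Censoring of DOR will follow the same algorithm as the censoring of PFS". Protocol Section 9.4.1.2 censors only for being alive without progression, leaving the study, starting other anticancer treatment and, for PFS, having no assessment.

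**Declaration and sensitivity analyses.** SAP Section 11.1, which is for changes to Protocol-defined analyses, is marked as not applicable. The planned sensitivity analysis concerns crossover: "A sensitivity analysis of PFS will be performed where response assessments after the time of crossover will be excluded from the determination of PFS". The one for DOR in Section 7.4.1 is parallel.

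**Outputs.** Medians are planned for both endpoints. For PFS, "Progression-free survival rates at Month 6, 12, 18, 24, and 36 will also be provided".

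**The concern.** A death before the first scan is among the worst outcomes a participant can have. Under one row it is a PFS event. Under another the participant leaves the risk set at Day 1, as if nothing were known. The same participant stays in the ORR and CRR denominators (SAP Sections 7.3.1 and 7.4.2). In an open-label study, a choice that the plan leaves open could be made after the data have been seen.

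There is a further overlap. Protocol Section 5.7 lists death as a reason for study discontinuation, and Table 2 has censoring rows for study discontinuation that do not exclude death.

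The missed-assessment row raises a different issue. It turns some Protocol-defined events into censored observations. The section where a reader would look for such a change says there is none, and no planned analysis shows how much the rule matters.

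**Working it through.** The documents give no PFS or DOR rate, event count or power, so there is no plan figure to reproduce. The check has two parts: the rules set side by side, then an illustration on assumed inputs.

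**1. Death at Week 5, no post-baseline scan** (first scan due at Week 8)

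| Rule | Result |
|---|---|
| PFS definition, both documents | Event, Week 5 |
| Table 2, death before progression | Event, Week 5 |
| Table 2, no valid post-baseline assessment | Censored, Day 1 |
| Protocol 1-day sentence | Censored, 1 day |

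If the death is at Week 20 with the Week 8 and Week 16 scans missed, the missed-assessment row applies too, and there is no earlier post-baseline scan to date it by. This part concerns PFS only, because a responder has a post-baseline assessment by definition.

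**2. Last valid scan Week 24, Weeks 36 and 48 missed, death at Week 55, on study, no new treatment.** Protocol: event at Week 55. SAP: censored at Week 24.

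**3. Size of the Day-1 reading.** N = 90 (planned Cohort 2 maximum). Assumed: 12-month PFS S with the early deaths counted as events, d such deaths, no other censoring before Month 12. Reported PFS = S × N/(N − d).

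- S = 70%, so 63 of 90 are event-free. For d = 1 to 4: 63/89 = 70.8%, 63/88 = 71.6%, 63/87 = 72.4%, 63/86 = 73.3%.
- 95% CI half-width: 1.96 × √(0.7 × 0.3/90) = 9.5 points.
- Range for d = 1 to 4: +0.6 to +2.3 points at S = 50%, and +0.9 to +3.7 points at S = 80%.
- Month 6 on the same exponential curve: 0.70^0.5 = 83.7% becomes 84.6% to 87.6%.

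**4. Size of the missed-assessment rule, PFS.** Assumed: 90 exponential-quantile event times with 12-month PFS of 70% and no other censoring before Week 160. On this curve 14 events precede Week 24, leaving 76 at risk, and 63, 53 and 44 participants are event-free at Months 12, 18 and 24. The m events nearest Week 55 are set at Week 55, then recoded as censored at Week 24. Reported PFS = (76/90) × a/(76 − m). Here a = 63 − m at Month 12, which lies inside the gap; a = 53 at Month 18 and 44 at Month 24.

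| m | Month 12 | Month 18 | Month 24 |
|---|---|---|---|
| 0 | 70.0% | 58.9% | 48.9% |
| 1 | 69.8% | 59.7% | 49.5% |
| 2 | 69.6% | 60.5% | 50.2% |
| 3 | 69.4% | 61.3% | 50.9% |

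**5. Same rule, DOR.** 54 responders (60% of 90), 12-month value 38/54 = 70.4%, first response at Week 8. Events at Week 47 after response (55 − 8) are recoded as censored at Week 16 (24 − 8), when 48 are at risk. Reported value = (48/54) × 38/(48 − m): 71.9%, 73.4% and 75.1% for m = 1, 2, 3. The half-width is 1.96 × √(0.704 × 0.296/54) = 12.2 points. SAP Section 7.4.1 plans the median and no DOR rate at fixed months, so these are readings from the planned Kaplan-Meier curve.

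**The case against.** The missed-assessment row is printed openly in Table 2, and SAP Section 7.4.3 names the FDA guidance behind it. Nothing is hidden, and the choice is legitimate. This stands: the row need not be dropped. What it leaves is a missing entry in Section 11.1 and a missing robustness run, because citing guidance does not tell the reader that the Protocol's rule was different.

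Early deaths without a scan should be few. Protocol Section 3.1 requires a life expectancy above 3 months, and Sections 6.4.2 and 7.6.1 continue imaging after treatment stops for reasons other than progression. A reader might infer that such deaths are certain to be in the data; the documents do not support that. Survival follow-up (Protocol Section 6.4.3) would capture them if they occur.

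A reader might also infer that missed-assessment censoring always inflates PFS. It does not: inside the gap the curve is slightly lower, as the Month 12 column shows.

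The shifts are smaller than the sampling error, every input is assumed, and the endpoints are secondary with no hypothesis test. All of that stands and limits the weight of the point. It does not settle which row applies.

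**Conclusion.** Both parts hold. A participant who dies before any valid post-baseline scan is an event under one rule and censored at Day 1 under another, with no precedence, and the Day-1 reading drops a PFS event. The missed-assessment rule for PFS and DOR is absent from Protocol Section 9.4.1.2, undeclared in SAP Section 11.1 and untested by the planned sensitivity analyses.

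On the assumed inputs, the first part adds about 0.8 to 3.3 points to a 12-month PFS of 70% for one to four deaths. The second adds 0.8 to 2.4 points at Month 18 for one to three participants and takes off 0.2 to 0.6 points at Month 12. Each effect is zero if no such cases occur.

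The documents do not support a reading that the primary result is at risk: ORR, CRR and OS do not use these rules. The change should be made, but the study's main conclusion does not depend on it.

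**What to change.** (a) In SAP Table 2, limit the two Day-1 rows to participants with no recorded death. Make the same change to the Protocol's 1-day sentence at its next amendment.

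(b) State one order under Table 2:

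1. Take the earlier of first documented progression and death.
2. If new anticancer treatment started, or the participant left the study alive, before that date, censor under the existing rows (at Day 1 if there is no baseline or no valid post-baseline scan).
3. If it follows two or more missed scheduled assessments, apply the missed-assessment row. State that this row needs at least one earlier valid post-baseline scan, so that a death with no such scan is an event at the date of death.
4. Otherwise it is an event at its own date. With no progression or death, the existing censoring rows apply.

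Also state that progression with no baseline assessment is not counted as a progression event. A later death in that participant is an event at the date of death, subject to step 2.

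(c) Replace the entry in SAP Section 11.1 with two: the missed-assessment rule for PFS and DOR, and the counting of no-scan deaths as PFS events. The second is needed because the Protocol's 1-day sentence, until amended, says otherwise.

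(d) Rerun SAP Tables 2.2.1 (DOR, IRC) and 2.2.3 (PFS, IRC) once without the missed-assessment row, labelled as a sensitivity analysis without missed-assessment censoring. Do not describe it as matching the Protocol until the 1-day sentence is amended.

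The cost is a few SAP lines and one extra run of two existing tables, with no stand-alone Protocol amendment. PFS and DOR may come out slightly lower.

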9.4.1.3. Other Efficacy Analyses

Analyses of ORR, DOR, CRR, and PFS as reported by the investigator will be summarized as described above.

Analyses of ORR, DOR, CRR, PFS as determined by IRC, and OS will also be summarized by treatment regimens (A or B) within each cohort.

9.4.2. Safety Analyses

9.4.2.1. Adverse Events

A TEAE is any AE either reported for the first time or worsening of a pre-existing event after first dose of study drug and within 30 days of the last administration of study drug. Analysis of AEs will be limited to TEAEs, but data listings will include all AEs regardless of their timing to study drug administration. Adverse events will be tabulated by the MedDRA preferred term and system organ class. Severity of AEs will be based on the NCI CTCAE v4.03 using Grades 1 through 5.

The subset of AEs considered by the investigator to have a relationship to study drug will be considered to be treatment-related AEs. If the investigator does not specify the relationship of the AE to study drug, the AE will be considered treatment-related. The incidence of AEs and treatment-related AEs will be tabulated.

Number (%) of subjects reporting any TEAEs, any SAEs, any Grade 3 or 4 TEAEs, any treatment-related TEAEs, any treatment-related SAEs, any treatment-related Grade 3 or 4 TEAEs, any fatal TEAE, and any TEAEs leading to treatment interruption/dose reduction/discontinuation will be summarized and tabulated by system organ class and preferred term.

